11.2 Adverse Events of Special Interest

A specific concern in treatment with botulinum toxin products is the potential for local and distant spread of toxin effect, a unique set of safety concerns related to use of botulinum toxin drug products (draft guidance for industry *Upper Facial Lines: Developing Botulinum Toxin Drug Products*). Therefore, subjects will be instructed and educated on possible warning signs and precautions and on rare AESIs through the Subject Information Sheet (SIS). Safety data related to this specific potential effect should be obtained through directed query at each study visit and if an AESI as below is reported a targeted physical examination should be conducted to evaluate for signs and symptoms of local and distant spread of toxin effect. Adverse events of special interest potentially suggestive of distant spread of toxin, include:

accommodation disorder	dyspnea	paresis
areflexia	extraocular muscle paresis	peripheral nerve palsy
aspiration	eyelid function disorder	peripheral paralysis
blurred vision	eyelid ptosis	pelvic floor muscle weakness
botulism	facial palsy	pneumonia aspiration
bradycardia	facial paresis	pupillary reflex impaired
bulbar palsy	fourth cranial nerve paresis	quadriparesis
constipation	hemiparesis	respiratory arrest
cranial nerve palsies	hypoglossal nerve paresis	respiratory depression
cranial nerve paresis	hyporeflexia	respiratory failure
cranial nerve paralysis	hypotonia	speech disorder
diaphragmatic paralysis	monoparesis	third cranial nerve paresis
diplopia	muscular weakness	trigeminal nerve paresis
dry mouth	paralysis	urinary retention
dysarthria	paralysis flaccid	vocal cord paralysis
dysphagia	paralytic ileus	vocal cord paresis
dysphonia	paraparesis	

The first AESI questioning will be undertaken (in accordance with the AESI Manual) prior to the first injection, in order to obtain a full baseline status of any concomitant diseases. If an AESI is reported, a targeted physical examination must be conducted. If reported during a telephone contact, subjects must come to the site for further assessment as soon as possible.

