11.6.1 Reporting Serious Adverse Events and Adverse Events of Special Interest

All SAEs and AESIs for all subjects occurring from the time of informed consent until the End of Study visit must be reported to CROMA Pharma GmbH or their representative **within 24 hours** of the knowledge of the occurrence. If considered at least possibly related to study treatment, SAEs observed after the End of Study visit must also be reported.

Paper SAE/AESI forms should be completed at the site and faxed to the relevant Medical & Safety Services Department [REDACTED] **within 24 hrs** of awareness of the event.

Fax number for SAE/AESI and Pregnancy reporting:

Email all sites:

[REDACTED]

For European sites

[REDACTED]

For North American sites

████████████████████

If the report is sent via email then the completed and signed SAE/AESI or Pregnancy report form must be attached to the email. A notification email of the event describing it in the email text is not sufficient.

There may be situations when an SAE/AESI has occurred and the investigator has minimal information to include in the initial SAE/AESI report to CROMA Pharma GmbH, or their representative. However, it is very important that the investigator always makes an assessment of causality for every event prior to transmission of the SAE/AESI report form. Minimum criteria are identifiable subject (number), a suspect product (i.e. IMP or concomitant medication), an identifiable reporting source (investigator/study-site identification) and an event or outcome that can be identified as serious or as an AESI. The investigator may change his/her opinion of causality in the light of follow-up information, amending the SAE/AESI report form accordingly. The causality assessment is one of the criteria used when determining regulatory reporting requirements for SAEs.

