Adverse events will be separated to pre-treatment AEs and TEAEs. TEAEs are defined as all AEs with onset or worsening (increase in severity) after receiving first dose of study medication (independent of whether it is BoNT/A-DP or placebo). If it cannot be determined whether an AE is treatment-emergent due to a partial onset date, then it will be counted as such.

TEAEs will be analyzed overall (for BoNT/A-DP or placebo), and for BoNT/A-DP treatment group additionally separately per first treatment cycle or open label extension phase: events starting on or after first treatment up to before open label extension (first cycle), and events starting on or after re-treatment until end of study (open label phase). If it cannot be determined whether an AE started during the first treatment cycle or the open label extension phase due to a partial onset date, then it will be counted as having started during first treatment cycle.

Events of subjects who started the first treatment with placebo but then entered the open label extension for re-treatment with BoNT/A-DP will be considered to placebo for the first cycle and to BoNT/A-DP for the open label phase.

Treatment-emergent adverse events will be summarized by system organ class (SOC) and preferred term (PT) (MedDRA). The number of events, as well as the number and rate of affected subjects will be reported. TEAEs (SOC and PT) will also be summarized by seriousness, severity, relationship to study medication, and relationship to procedure. Treatment-emergent AESIs will be tabulated separately.

Analysis of secondary safety endpoint 2 (antibody formation):

The presence of antibodies will be summarized by counts and percentages of subjects by treatment group and time point. For the subgroup of subjects with a sample test positive for anti-drug antibodies, all analyzed samples will be analyzed descriptively by counts over time as well.

Analysis of secondary safety endpoint 3 (laboratory data, vital signs, ECG):

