8.7.2 Adverse events (secondary safety endpoint 1)

All AEs will be classified by SOC and PT according to MedDRA Version 19.0 or higher.

In summaries by SOC and PT, adverse events will be sorted by decreasing frequency within each SOC and PT. In summaries by PT, AEs will be sorted by decreasing frequency within each PT.

AE summary tables will be presented for TEAEs and AESIs separately by treatment cycle and will include the number and percentage of subjects with any:

- TEAE/AESI
- TEAE/AESI related to study medication (AE will be defined as related if causality is definitely, probably or possibly or if causality assessment is missing)
- TEAE/AESI related to injection procedure (AE will be defined as related if causality is definitely, probably or possibly or if causality assessment is missing)
- Severe TEAE/AESI

Statistical Analysis Plan (SAP)

- Severe TEAE/AESI related to study medication
- Severe TEAE/AESI related to injection procedure
- TEAE/AESI leading to discontinuation
- Study drug related TEAE/AESI leading to discontinuation
- Serious TEAE/AESI
- TEAE/AESI leading to death.

All TEAEs as well as all AESIs will be summarized by SOC, PT and treatment group using frequency counts and percentages (i.e. number and percentage of subjects with an event).

The number of events, as well as the number and rate of affected subjects will be reported by SOC and PT for all TEAEs and for all AESIs separately.

Adverse events will be separated to pre-treatment AEs and TEAEs. TEAEs are defined as all AEs with onset or worsening (increase in severity) after receiving first dose of study medication (independent of whether it is BoNT/A-DP or placebo). If it cannot be determined whether an AE is treatment-emergent due to a partial onset date, then it will be counted as such.

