TEAEs and AESIs will be analyzed overall (for BoNT/A-DP or placebo), and for BoNT/A-DP treatment group additionally separately per first treatment cycle or open label extension phase: events starting on or after first treatment up to before open label extension (first cycle), and events starting on or after re-treatment until end of study (open label phase). If it cannot be determined whether an AE started during the first treatment cycle or the open label extension phase due to a partial onset date, then it will be counted as having started during first treatment cycle. The assignment of AEs to the different cycles of the open label extension phase will be done similarly: AEs will be assigned to a certain cycle if they start on or after treatment of the respective cycle but before treatment of the next cycle. In case that there is no subsequent treatment cycle, all AEs (starting on or after the last treatment) until end of study will be assigned to the last cycle.

Events of subjects who started the first treatment with placebo but then entered the open label extension for re-treatment with BoNT/A-DP will be considered to placebo for the first cycle and to BoNT/A-DP for the open label phase.

TEAEs and AESIs (per SOC and PT) will also be summarized by seriousness, severity, relationship to study medication, and relationship to procedure using frequency counts and percentages (i.e. number and percentage of subjects with an event).

Statistical Analysis Plan (SAP)

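### The SAP's overall AESI tables carry no treatment-emergent limit, although the protocol plans treatment-emergent AESIs and the change is not declared

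*SAP*

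**What the plan says.** **Analysis.** Protocol 12.4.2, under secondary safety endpoint 1, divides adverse events into pre-treatment events and TEAEs, summarises the TEAEs, and adds: "Treatment-emergent AESIs will be tabulated separately".

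SAP 8.7.2 keeps the division ("Adverse events will be separated to pre-treatment AEs and TEAEs") and defines a TEAE as an event that starts, or increases in severity, after the first dose. Its tables then treat the two groups differently. TEAEs are limited by their definition. AESIs are not: "All TEAEs as well as all AESIs will be summarized by SOC, PT and treatment group using frequency counts and percentages". Numbers of events and of affected subjects "will be reported by SOC and PT for all TEAEs and for all AESIs separately". The SAP does not define a treatment-emergent AESI.

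Two sets of AESI tables do depend on timing. The overview is by cycle ("AE summary tables will be presented for TEAEs and AESIs separately by treatment cycle"). The split by phase takes first-cycle events to be "events starting on or after first treatment up to before open label extension (first cycle").

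SAP section 9 lists two changes from the protocol: the safety set definition and the antibody analysis. It does not mention AESIs.

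**Collection.** Protocol 11.2 states: "The first AESI questioning will be undertaken (in accordance with the AESI Manual) prior to the first injection". Protocol 11.6.1 states: "All SAEs and AESIs for all subjects occurring from the time of informed consent until the End of Study visit must be reported". Protocol 11.1 says both that AEs are recorded from signature of the consent form and that events between consent and first dose go on the Medical History page as pre-treatment events.

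**The concern.** Local and distant spread of toxin is the safety question that the protocol singles out (Protocol 4.6.2 and 11.2), and the AESI tables are where a reader will look for it. Safety results are descriptive only, so the tabulated rates carry the message.

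The SAP's wording allows an event that began before any injection to be counted under BoNT/A-DP or placebo. Subjects are asked about AESIs before the first injection, and several listed terms are everyday complaints (constipation, dry mouth, blurred vision). Events that precede treatment say nothing about treatment. Counting them raises the absolute rate in both arms and moves the ratio of the two rates towards 1.

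**Working it through.** The documents give no AESI rate, so there is no planned figure to reproduce. The check is mainly a comparison of texts.

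**1. Which tables are exposed?**

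| AESI table in SAP 8.7.2 | Onset limit stated? |
|---|---|
| Overview by treatment cycle | Yes, through the rule that assigns events to cycles |
| First cycle versus open label phase | Yes, onset on or after the treatment concerned |
| By SOC, PT and treatment group | No |
| Overall, BoNT/A-DP or placebo | No |
| By seriousness, severity, relationship | No |

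The by-phase sentence is written for the BoNT/A-DP group. Taking it as the definition of the first cycle in both arms is the natural reading.

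**2. Would a pre-dose AESI be in the data that feed these tables?**

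- Against: Protocol 11.1 sends events between consent and first dose to Medical History, reserves the AE record for events after first dose, and says that remarks on AEs also apply to AESIs.
- For: the same section has AEs recorded from consent, Protocol 11.6 monitors AEs from consent, and 11.6.1 requires AESI reports from consent.
- For: the SAP expects such records. SAP 8.7.2 separates pre-treatment AEs from TEAEs, and the start-date imputation in SAP 7.2.2.1 exists partly to decide which of the two an event is. Neither step would be needed if Medical History had already taken every pre-dose event.

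The documents do not settle the question.

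**3. Which events could be affected?** Conditions present before consent are Medical History and become AEs only if they worsen (Protocol 11.1 and 11.8). That leaves new onsets, or worsening, between consent and first injection. Screening lasts at most 14 days.

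**4. Direction and scale, on assumed rates.** Let *a* and *p* be the post-dose rates in one table row for active and placebo, and *b* the share of subjects with a pre-dose event in that row. Assume that *b* is the same in both arms, is independent of post-dose events, and is wholly counted. Then:

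- tabulated active rate = 1 − (1 − a)(1 − b)
- tabulated placebo rate = 1 − (1 − p)(1 − b)
- difference = (a − p)(1 − b)

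For example, with a = 5%, p = 1%, b = 1%: active 1 − 0.95 × 0.99 = 5.95%; placebo 1 − 0.99 × 0.99 = 1.99%; difference 3.96 points; ratio 2.99.

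| a vs p (assumed) | b (assumed) | Active | Placebo | Difference (points) | Ratio |
|---|---|---|---|---|---|
| 5% vs 1% | 0 | 5.00% | 1.00% | 4.00 | 5.00 |
| | 1% | 5.95% | 1.99% | 3.96 | 2.99 |
| | 2% | 6.90% | 2.98% | 3.92 | 2.32 |
| | 5% | 9.75% | 5.95% | 3.80 | 1.64 |
| | 10% | 14.50% | 10.90% | 3.60 | 1.33 |
| 3% vs 1% | 0 | 3.00% | 1.00% | 2.00 | 3.00 |
| | 10% | 12.70% | 10.90% | 1.80 | 1.17 |
| 10% vs 2% | 0 | 10.00% | 2.00% | 8.00 | 5.00 |
| | 10% | 19.00% | 11.80% | 7.20 | 1.61 |

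The difference shrinks only by the factor (1 − b). The ratio is more sensitive, chiefly when *b* is as large as the placebo rate. Nothing in the documents supports any particular *b*. The upper values are there to show the range; for new onsets of a single term within 14 days they would be high.

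**The case against.** The strongest reply is that the data rules already keep pre-dose AESIs out. Protocol 11.1 routes them to Medical History and extends AE rules to AESIs. Protocol 11.2 gives the purpose of the pre-injection questioning as establishing baseline status, which guards against miscounting. The reporting duty in 11.6.1 concerns notification of the sponsor, not the content of tables. The opening of SAP 8.7 limits the safety analyses to the double-blind and open label treatment periods. The protocol does not say that only treatment-emergent AESIs may be tabulated, and safety endpoint 1 covers the whole study period.

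Much of this stands, and it limits the size of the problem. It does not close the gap. The recording rules contradict each other, and the schedule in Protocol 2.1 places screening under the double-blind heading, so the scope sentence in SAP 8.7 is not decisive. The endpoint's time window also does not override the analysis that 12.4.2 specifies for it.

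Two stronger readings are tempting, and the documents support neither.

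- A reader might infer that pre-dose events would hide a toxin-spread signal. The risk difference barely moves, the by-cycle and by-phase tables stay clean, AESIs are also shown by severity and relationship, and no safety test is planned that could lose power.
- A reader might add a pre-dose rate for any listed term to the eyelid ptosis rate in the earlier glabellar line study HG-11-01 (6 of 134). In a table by preferred term, pre-dose constipation or dry mouth sits in its own row and leaves the ptosis row unchanged. Eyelid ptosis is also an exclusion criterion (Protocol 7.2).

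**Conclusion.** The mismatch is real and undeclared: treatment-emergent AESIs in the protocol, all AESIs in the SAP. It matters only for the tables without an onset limit, only for events that are new or worse between consent and first injection, and only if those events are entered in the AE data. Under those conditions the absolute AESI rates would be modestly inflated in both arms and the ratio diluted to some degree. The amount cannot be stated from the documents, and the figures above rest on assumed rates. Severity is minor: a plan that should be made to say what the protocol says, not a demonstrated bias.

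**What to change.** 1. In SAP 8.7.2, limit every AESI table to treatment-emergent AESIs, using the onset-or-worsening rule already given for TEAEs.
2. Add one listing of AESIs with onset before the first injection, presented as baseline status.
3. Reconcile Protocol 11.1 with 11.6.1, and with the pre-treatment AE handling in SAP 7.2.2.1 and 8.7.2, so that one rule says where a pre-dose AESI is recorded.
4. If the sponsor does intend to tabulate all AESIs, declare it in SAP section 9 with a reason and show pre-dose events outside the treatment-group rates.

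The cost is wording and one listing. No new data are needed, since onset and first-dose dates are already used to classify TEAEs. AESI counts would be the same or slightly lower.

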3.3 Study treatments and assessments

Subjects will participate in this study for a duration of 50 to 62 weeks from signing the informed consent form (ICF) to the End of Study visit (i.e. up to 14 calendar days for screening, followed by 48 to 60 weeks study participation).

The first treatment cycle of the study will comprise two treatment groups as follows:

- Group A (active): BoNT/A-DP (20 units, 0.5 mL).
- Group B (placebo control): sterile, 0.9% sodium chloride (0.5 mL).

Eligible subjects will be randomized at baseline (day 0) to Group A or B to receive the first treatment in a 3:1 randomization scheme, respectively. Investigators and subjects will be blinded to the treatment administered and will evaluate the severity of glabellar lines independently. The subjects must perform their assessment independently and ideally before the investigator, to ensure they are not biased by the investigator. The same investigator must assess the subject at baseline and at the visits at weeks 1, 2 and 4 in the first treatment cycle.

After a screening period of up to 14 calendar days, subjects will receive the first treatment (BoNT/A-DP or placebo) and attend for visits at 1, 2 and 4 weeks after treatment and at 4-weekly intervals thereafter for evaluation of efficacy and safety (primary and key secondary efficacy endpoints will only be evaluated in the first treatment cycle in comparison with placebo). Re-screening will not be permitted.

Statistical Analysis Plan (SAP)

The effect of botulinum toxin typically lasts a few months, hence the first treatment cycle will last at least 12 weeks and will end when the subjects qualify for re-treatment.

After the first treatment cycle is completed, all subjects may enter the open label extension phase and will be dosed with BoNT/A-DP (20 U) for subsequent re-treatments.

Subjects will attend for visits at one and four weeks after re-treatment and at 4-weekly intervals thereafter. Additional telephone call follow-ups will take place in the open label extension phase two and eight weeks after each re-treatment. Each re-treatment cycle will last at least 12 weeks and will end when the subject qualifies for re-treatment or with the End of Study visit. According to the study schedule, a maximum of four treatments per subject (four treatment cycles) is permitted during the study time frame, with treatments separated by a minimum of 12 weeks.

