5 SAMPLE SIZE AND POWER

The primary endpoint is a composite endpoint comprising investigator and subject assessments of treatment effectiveness using the FWS. The FWS in this study corresponds to the FWS Investigator assessment (GLS-I) and the FWS for Subject self-assessment (GLS-S). Composite endpoint treatment success (CETS) is defined as ≥ 2 point reduction in FWS score at maximum frown achieving a score of 0 or 1 at the visit week 4 relative to baseline based on investigator assessment and subject assessment. Thus, a subject is a CETS “responder” only if both investigator- and subject-rated success criteria are satisfied at the visit 4 weeks after baseline.

The primary analysis of efficacy is the proportion of responders in the BoNT/A-DP treatment group compared with the placebo treatment group. For superiority testing of BoNT/A-DP compared with placebo, the following assumptions for the sample size calculation are used:

Statistical Analysis Plan (SAP)

Item	Assumption	Comments
Underlying test	Fisher's Exact Test	Standard test for a response parameter for small numbers
Randomization scheme	3:1	More active treatment subjects to enlarge safety data base
Power 1- β	90%	
Significance level (α)	0.025 one-sided	
Response Arm BoNT/A-DP	60%	From the range of observed response rates, a more conservative value of 60% has been chosen
Response Arm Placebo	10%	Conservative value
Software		The sample size calculation was performed using the software nQuery Advisor® 7.0.

Based on these assumptions, 42 subjects in the BoNT/A-DP arm and 14 subjects in the placebo arm are required, i.e. 56 subjects in total. This is a very small sample size and not sufficient for a detailed evaluation of the data, including subgroup analyses. Furthermore, the response rate could not be estimated with sufficient precision. A two-sided confidence interval (CI) of 95%, and a distance from the CI limit of about 4.5% could be achieved with a sample size of 450 subjects in the BoNT/A-DP group. Therefore, a 3:1 randomization of BoNT/A-DP (525 subjects) to placebo (175 subjects) was proposed, which should be adequate for a precise estimate of response rate and for post-hoc sensitivity analyses (i.e. treatment-by-center and other subgroup analyses), also taking into account a drop-out rate.

In total, 700 evaluable subjects will be enrolled. Applying a 10% drop out rate would result in a total number of about 630 subjects.

Statistical Analysis Plan (SAP)

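### The planned overall adverse event analysis sets BoNT/A-DP follow-up over all cycles, including placebo switchers' open-label time, against placebo follow-up that stops at cycle 1

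*SAP*

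**What the plan says.** - SAP 8.7.2: "TEAEs and AESIs will be analyzed overall (for BoNT/A-DP or placebo". Protocol 12.4.2 has the same rule: "TEAEs will be analyzed overall (for BoNT/A-DP or placebo), and for BoNT/A-DP".
- The split by phase comes on top of this, "for BoNT/A-DP treatment group additionally separately per first treatment cycle or open label extension phase".
- Events of placebo subjects who are re-treated in the extension "will be considered to placebo for the first cycle and to BoNT/A-DP for the open label phase".
- The measures are the number and percentage of subjects with an event, and the number of events. No rate per subject-time is planned.
- The same SAP section also says "AE summary tables will be presented for TEAEs and AESIs separately by treatment cycle". Its tables by system organ class and preferred term (SOC/PT) are specified by treatment group, and further tables by seriousness, severity and relationship. None of these has a stated cycle limit.
- The protocol synopsis (General Statistical Considerations) describes separate first-cycle and open-label analyses and mentions no pooled overall one.
- On timing, SAP 3.3 says "the first treatment cycle will last at least 12 weeks and will end when the subjects qualify for re-treatment", with 48 to 60 weeks of participation after screening.
- SAP 8.7 makes safety descriptive, with no between-group testing.

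**The concern.** Taken together, the overall analysis and the attribution rule give two results that do not cover the same period. BoNT/A-DP holds up to four cycles of the subjects randomized to it, plus the open-label cycles of placebo subjects who switch. Placebo holds one double-blind cycle. A switcher can contribute to both. With crude percentages, the group followed longer shows more subjects with an event even if the drug does nothing.

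Side by side, the overall figures are therefore not a randomized comparison. They also mix blinded reports with reports from subjects who know they received toxin. The distortion runs against BoNT/A-DP, and it is proportionally largest for uncommon events, which include individual AESIs. One stated objective of the study is to build a safety database to support approval.

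**Working it through.** The plan gives no figure for the overall percentages, so there is none to reproduce. The check asks what the display would show if the drug had no effect.

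**Inputs from the documents**
- Arm sizes: "a 3:1 randomization of BoNT/A-DP (525 subjects) to placebo (175 subjects) was proposed" (SAP 5).
- Follow-up after first treatment, T: 48 to 60 weeks (SAP 3.3).
- Placebo cycle 1 length, c: at least 12 weeks with no fixed end (SAP 3.3).
- Event rate: 38 of 134 BoNT/A-DP subjects (28.4%) had an adverse event in the earlier glabellar-line trial (protocol 4.4.2.1), with 16 weeks of follow-up (protocol Table 4-2).

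**Assumptions**
- The event rate is constant and the same on both treatments.
- All placebo subjects switch, and nobody drops out.
- The denominator of the overall BoNT/A-DP result, which the SAP does not state, is 525 + 175 = 700.

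**Formulas**
- Weekly rate: λ = −ln(1 − 38/134)/16 = 0.0208.
- Probability of at least one event in t weeks: P(t) = 1 − exp(−λt).
- Placebo: P(c).
- BoNT/A-DP overall: [525 × P(T) + 175 × P(T − c)]/700 = 0.75 × P(T) + 0.25 × P(T − c).

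**Example, c = 12 and T = 48**
- P(12) = 22.1%, P(48) = 63.2%, P(36) = 52.8%.
- BoNT/A-DP overall = 0.75 × 63.2% + 0.25 × 52.8% = 60.6%.
- Ratio = 60.6/22.1 = 2.74.

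| Placebo cycle 1 | Placebo | BoNT/A-DP overall, end at week 48 to 60 | Ratio | Ratio of mean time at risk |
|---|---|---|---|---|
| 12 weeks | 22.1% | 60.6% to 69.3% | 2.74 to 3.13 | 3.75 to 4.75 |
| 16 weeks | 28.4% | 59.6% to 68.5% | 2.10 to 2.42 | 2.75 to 3.50 |
| 20 weeks | 34.1% | 58.5% to 67.7% | 1.72 to 1.98 | 2.15 to 2.75 |

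The last column is the limit for rare events. For c = 12 it is (0.75 × 48 + 0.25 × 36)/12 = 45/12 = 3.75, and at week 60 it is 57/12 = 4.75.

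**Sensitivity**
- A denominator of 525 without switchers, c = 12: 2.86 to 3.22.
- 10% of subjects leaving after cycle 1, c = 12, T = 48: 2.61.
- Unequal individual risk (gamma frailty, variance 1 to 2): 2.23 to 2.71 at c = 12, and 1.79 to 2.14 at c = 16.
- Risk tied to injections, at an assumed 9% each: 3.30 with four injections (three BoNT/A-DP injections in switchers), 2.53 with three (two), and 1.91 with two (two).
- With c = 12, the ratio falls below 2 once the placebo percentage exceeds about 44% (end at week 48) or 48% (end at week 60).

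**After correction**
- With both arms cut at week 12, the percentages are 22.1% and 22.1%, ratio 1.00. Per subject-time, both are 2.08 events per 100 subject-weeks.
- A cycle 1 table without a common cut-off keeps some imbalance. Suppose BoNT/A-DP cycles average 17.1 weeks (a duration of effect cited in protocol 6.3.1, used here as an assumption) and placebo cycles 12 weeks. Then the percentages are P(17.1) = 30.0% and 22.1%, a ratio of about 1.4.

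**The case against.** The strongest reply is that most of the remedy is already in the plan. SAP 8.7.2 has summary tables by treatment cycle, not restricted to BoNT/A-DP. Under the attribution rule placebo events exist only in cycle 1, so a phase split is needed only for BoNT/A-DP, and its first-cycle result can be read against the placebo result. The protocol synopsis points the same way. The table shells are in a separate document, so the two-column layout and its denominator are inferred. Nothing is tested.

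Much of this stands. A reader might infer that the plan offers no near like-for-like comparison, and the by-cycle tables show that it does. A reader might also infer that an error rate or decision rule is affected, but SAP 8.7 is purely descriptive.

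The reply does not remove the point. The cycle wording is attached to the summary tables. The SOC/PT tables, where individual events appear, and the seriousness, severity and relationship tables carry no stated cycle limit. The SAP never names cycle 1 as the between-group comparison. Changing the unstated denominator to 525 does not bring the ratio near 1. The planned exposure variable (SAP 7.1 and 8.5.1) cannot supply follow-up time: last minus first administration plus one day equals 1 day within a single-treatment cycle.

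**Conclusion.** The point holds for the overall display and for the adverse event and AESI tables without a stated cycle limit. Followed as written, the rules give BoNT/A-DP a higher crude percentage than placebo with no drug effect. The central estimate is a ratio of 2.7 to 3.1, and it rests on a constant event rate taken from the earlier glabellar-line trial and a 12-week placebo cycle.

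A reader might infer that BoNT/A-DP will always show more than twice the placebo percentage. The documents do not support that. The factor depends on the assumed rate, the placebo cycle length and the number of re-treatments. It falls below 2 with a 20-week placebo cycle (1.7 to 2.0), with only two injections per subject (1.91), or with a high placebo incidence. Nor does every subject contribute time to week 60, since follow-up ends between weeks 48 and 60. The consequence is a misleading safety display, not an invalid test.

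**What to change.** In SAP 8.7.2 and protocol 12.4.2:

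1. Name the double-blind first cycle as the only BoNT/A-DP versus placebo comparison for all adverse event and AESI tables, including those by SOC/PT, seriousness, severity and relationship.
2. Show overall and open-label BoNT/A-DP results as single-arm tables without a placebo column, and state the denominator.
3. Add events per subject-time, using a defined follow-up time that runs from the first treatment of the period to the end of the cycle or the end of study. The exposure variable in SAP 8.5.1 should not be used for this.
4. Use the subject-time rates, or a common week-12 cut-off, to deal with the remaining difference in cycle 1 length.

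The cost is SAP and protocol wording, revised table shells and one extra derived variable. No new data are needed.
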